## 10.5 Randomisation methods

No randomisation will be employed in this pilot study due to practical and ethical considerations.

A statistically powered RCT would be ideal to define the magnitude of benefit and impact on overall survival and is the typical design in patients with ARDS. Although there is clinical data on the safety of nebulised rtPA, but there are no clinical data on this condition to facilitate a sample size calculation. There are data from a small RCT that has used another fibrinolytic agent, but the doses are not comparable (Abdelaal Ahmed Mahmoud et al. 2020). If a patient is randomised to receive no treatment, this precludes participation in other interventional studies which might increase the risk of mortality. The most recent figures suggest a 50% mortality in patients receiving

IMV. (<https://www.icnarc.org/About/Latest-News/2020/04/04/Report-On-2249-Patients-Critically-III-With-Covid-19>) Currently there is a concerted effort to introduce multiple therapies based on our understanding of the pathophysiologic basis of disorder. Ethical concerns were raised about the potential for denying patients new treatment strategies when randomised to standard of care arm. The management strategies are evolving on an unprecedented scale with repurposing of existing medications, many of which are proof of concept of studies. Further, if this pilot study shows significant effect in a subset of patients, there would be justification to progress to a statistically powered RCT. We would progress to a RCT only after submission of a substantial amendment to this trial protocol or submission of a new clinical trial application. In the event of major adverse drug reactions or minor improvement in the oxygenation as assessed by  $\text{PaO}_2/\text{FiO}_2$ , there are minimal gains to be had with a larger randomised control study.

A Data Monitoring Committee (DMC) will be set-up to review safety data within the trial along with the final study results and advise on progressing from a pilot study to a statistically powered RCT based on the safety and efficacy data that is collected.

## 10.6 Statistical analysis plan

All analyses will be descriptive in nature and should be considered as hypothesis generating rather than providing firm conclusions.

Analysis of cohorts 1 and 2 will be undertaken separately.

All study data will be listed and all relevant data will be tabulated and summarised separately by cohort and by group (rtPA treated, historical controls), separately for the patients receiving IMV, and for other patients with mild ARDS requiring non-invasive oxygen support at enrolment, and overall only where appropriate, as follows:

Planned recruitment for Cohort 1:

Group 1: Patients with ARDS receiving IMV at enrolment treated with rtPA (n=6)

Group 2: Patients with ARDS requiring non-invasive support at enrolment treated with rtPA (n=6)

Group 3: Patients with ARDS receiving IMV - historical controls (n=12)

Group 4: Patients with ARDS requiring non-invasive support - historical controls (n=12)

Planned recruitment for Cohort 2:

A total of 30 patients will be recruited, with a minimum of 10 from each ventilation type.

Group 5: Patients with ARDS receiving IMV at enrolment treated with rtPA

Group 6: Patients with ARDS requiring non-invasive support at enrolment treated with rtPA

Data will be presented using standard descriptive statistics. Continuous variables will be summarised using number of observations, mean, and standard deviation, median, inter-quartile range, minimum, and maximum values. Categorical values will be summarised using number of observations and percentages.

A statistical analysis plan will be written and finalised prior to database lock. This plan will give a detailed description of all summaries and results that will be presented. Cohort 1 data will be locked separately from the cohort 2 data and a separate SAP will be produced for the analysis of the cohort 2 data.

### **10.6.1 Summary of baseline data and flow of participants**

All pre-treatment assessments data in the protocol will be listed and all relevant data will be tabulated for each group separately.

For patients treated with rtPA + SOC, the last available value prior to the first administration of IMP will be considered the baseline value.

For patients receiving SOC only (historical controls), the last available value prior to enrolment, as defined in section 8.2, will be considered the baseline value.

All data necessary to produce a consort flow diagram (<http://www.consort-statement.org/>) will be summarised: the number of patients in each group that were enrolled, assessed for eligibility, excluded (with reasons listed), assigned to a group, treated with rtPA + SOC, followed up, discontinued (with reasons such as lost to follow-up, withdrawn, or death), and number of patients analysed in each group, and where applicable excluded from analyses (with reasons).

### **10.6.2 Primary outcome analysis**

The PaO2/FiO2 ratio measured over time will be described for each group. The change from baseline in the PaO2/FiO2 ratio will be summarised at each post baseline timepoint. Plots will be used, where appropriate, to show the PaO2/FiO2 summarised for patients over time.

PaO2/FiO2 will be a calculated field on the trial database derived from the fields for PaO2 and FiO2. For cohort 2 data will be extracted once a day coinciding with the worst PF ratio. As PF ratio is the primary endpoint, in addition to the worst PF ratio, up to a maximum of 6 data points spread across 24 hrs that represents patients clinical status will be extracted. Details of further data derivation and analyses will be described in the SAP.

All patient data will be used, regardless of any intercurrent events that may have occurred after enrolment:

- Data from patients recruited into the rtPA + SOC group will be summarised whether or not patients have received all planned doses of the IMP.
- Any change in requirement for oxygenation and ventilation support will be summarised and described
- Changes in PaO2/FiO2 ratio over time will be described and interpreted taking into consideration that a patient's condition may have changed and led to their ventilation type changed post enrolment. If data allows, additional descriptions of the PaO2/FiO2 ratio over time may be performed in each subgroup of patients experiencing such changes (e.g. IMV to NIV, or vice versa).

The incidence and severity of bleeding events will be summarised in each group, and the change in fibrinogen levels will also be summarised at each post-baseline timepoint.

For cohort 1, subject to the final sample size and data quality, outcomes will also be compared between the SOC only group and intervention (rtPA + SOC) group using appropriate regression methods to make adjustment for baseline characteristics. Appropriate data transformations required for model assumptions will be considered if necessary.

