## 7 Trial procedures

### 7.1 Pre-treatment Assessments

#### 7.1.1 Screening – Cohorts 1 and 2

The results from the following routine procedures may be used to assess the participant's eligibility. Where routine results are not available at the time of consent, the procedure(s) will be carried out after consent. All must have been done within 24 hours prior undertaken as part of their standard care before their first dose of rtPA. These will also constitute the baseline assessments for cohort 2.

Patients receiving rtPA and SOC will undertake all assessments:

- Informed consent
- Demographics
- Review of medical history (including inpatient history and COVID-19 diagnosis – see section 7.7).
- Eligibility review
- Pregnancy test (blood or urine) for female participants of childbearing potential
- Concomitant medications
- Directed physical examination including vital signs (heart rate, temperature, blood pressure, and body weight)
- Documentation of respiratory status: Respiratory status of patients is monitored hourly and data points will be extracted for every four hour where available, but one data point is required as a minimum. The time of measurement should be documented. The variables include:
  - Details of oxygen and respiratory support including the type of device and FiO2  
Respiratory rate
  - PaO2
  - For IMV patients, details of ventilation including but not exclusively the below
    - Tidal volume (in mL)
    - Full sedation or not – not for cohort 2
    - Paralysis or not – not for cohort 2
    - Patient position – not for cohort 2
    - Peak inspiratory pressure (for computing compliance)
    - PEEP (for computing compliance )

- For non-invasive support patients:
  - SpO2
  - Oxygen flow rate
  - National Early Warning Score (NEWS 2) – not for cohort 2
- For CPAP patients
  - Positive end expiry pressure (PEEP)
- Local blood testing as per section 7.6.2
- Research blood sampling as per section 7.6.2
- Clinical status as assessed by 7-point ordinal scale (see section 7.7)
- Sequential Organ Failure Assessment (SOFA) score (see section 7.7)
- Glasgow coma scale (see section 7.7)

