## 7.5 Visit schedule and assessments post initiation of treatment

### 7.5.1 Cohort 1 and 2

Any assessments that are done as per routine care do not need to be repeated.

- Documentation of respiratory status: Respiratory status of patients is monitored hourly and data points will be extracted for every four hours where available until 5 days after the last dose for cohort 1, but one data point per day is required as a minimum. For cohort 2 data will be extracted once a day coinciding with the worst PF ratio. As PF ratio is the primary endpoint, in addition to the worst PF ratio over the preceding 24 hrs up to a maximum of 6 data points spread across 24 hrs that represents patients clinical status will be extracted. Similar to cohort 1 respiratory data will be collected until 5 days after the last dose. After this period, respiratory status is to be documented weekly (+/- 1 day) until discharge, death, or 28 days whichever occurs first. The time of measurement should be documented.
- The variables include:
  - Details of oxygen and respiratory support including the type of device, FiO2 Respiratory rate
  - PaO2
  - For IMV patients, details of ventilation including but not exclusively the below
    - Tidal volume (in mL)
    - Full sedation or not – not for cohort 2
    - Paralysis or not – not for cohort 2.
    - Patient position – not for cohort 2
    - Peak inspiratory pressure (collected for computing compliance)
    - PEEP (collected for computing compliance)
  - For non-invasive oxygen support patients:
    - National Early Warning Score (NEWS 2) – not for cohort 2
    - Oxygen flow rate
    - SpO2
  - For CPAP patients
    - Positive end expiry pressure (PEEP)

The following tests are to be done at a minimum once a day until 5 days after the last dose (day 7 for SOC patients) in cohort 1, a minimum every other day in cohort 2, and then as required until day 28, discharge or death whichever occurs first.

- Local blood testing as per section 7.6.2

The following tests will be done once at 48 h (+/- 24 h) and 96 h (+/- 24h) after start of treatment and then twice weekly while on treatment until 5 days after stopping treatment. After this period, testing should be weekly (+/- 1 day) until day 28, discharge or death whichever occurs first. Twice weekly testing should be evenly spaced across weekdays if possible.

- Research blood sampling as per section 7.6.2

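### In cohort 2 the daily P/F is the worst value plus an optional, hand-picked set of readings, while baseline is the last pre-dose value; one fixed-time rule should apply before and after dosing

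*Protocol*

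**What the plan says.** **After dosing.** Protocol 10.6.2 says of cohort 2: "For cohort 2 data will be extracted once a day coinciding with the worst PF ratio". It adds that "up to a maximum of 6 data points spread across 24 hrs that represents patients clinical status will be extracted". Section 7.5.1 and Appendix 1 footnote a give the same rule and specify the window: "in addition to the worst PF ratio over the preceding 24 hrs up to a maximum of 6 data points". None of the three sets a minimum number or clock times for the extra readings.

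**Before dosing.** Protocol 10.6.1 says that for treated patients "the last available value prior to the first administration of IMP will be considered the baseline value". Section 7.1.1 asks for respiratory readings every four hours where available, with one as the minimum, and does not ask for the worst value. Of these screening assessments it says: "These will also constitute the baseline assessments for cohort 2".

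**Derivation.** Section 10.6.2 defers: "Details of further data derivation and analyses will be described in the SAP". Section 10.6 says that "a separate SAP will be produced for the analysis of the cohort 2 data". The supplied SAP (version 1.0) cites protocol version 7.0. Cohort 2 was added in version 8.0, so that SAP does not cover it.

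**Cross-reference.** The primary endpoint (Summary and 10.1.1) defines baseline by sections 7.1.2 and 7.1.3. Section 7.1.2 is headed as applying to cohort 1 only, and there is no 7.1.3.

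**The concern.** Change from baseline is easiest to interpret when both ends are measured in the same way. Here the only reading required on every post-dose day is a daily minimum, while baseline is one unselected reading. The other readings on offer are chosen by staff, in an open-label trial (4.1), as representing the patient.

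Either route can move the primary efficacy summary without any drug effect, and cohort 2 has no concurrent or historical controls to absorb the shift. No error rate is at stake, because the analyses are descriptive. But Protocol 10.5 says that only a minor improvement in P/F would leave little to gain from a larger randomised trial, and under 12.2 the DMC advises on progression from these data. An artefact in the mean change could therefore colour that advice.

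**Working it through.** The plan gives no numerical figure for this point, so there is none to reproduce. The check sizes the two possible routes.

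**Inputs.** From the documents: baseline is the last pre-dose value (10.6.1); the post-dose value is the worst of 24 h or some of at most six others (7.5.1, 10.6.2); entry requires P/F of 300 or less (6.1.1). Assumed, because the documents give none of these: within-day SD 20 to 40 mmHg, correlation between readings 4 h apart of 0 to 0.9, true patient mean 200 to 275 mmHg, and between-patient SD 30 to 50 mmHg.

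**Route 1: worst of six minus last, no true change.** With independent readings in within-day SD units, the expected minimum of k readings is −∫ x·k·φ(x)·Φ(x)^(k−1) dx. At k = 6 this is −1.27. The unselected baseline reading has expectation 0, so the spurious change is −1.27 SD. With first-order autoregressive correlation within the day (simulation):

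| 4-hourly correlation | Worst of 6 minus last (SD units) |
|---|---|
| 0 | −1.27 |
| 0.7 | −0.89 |
| 0.9 | −0.55 |

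In mmHg the range runs from 0.55 × 20 = 11 to 1.27 × 40 = 51 too low.

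**Offset from the entry rule.** Suppose the eligibility reading is also the last pre-dose reading and is independent of post-dose days. Selection at 300 or less then makes later readings rise on average by (σw²/s)·φ(a)/Φ(a), where s = √(σb² + σw²) and a = (300 − μ)/s.
- μ = 275, σb = 30, σw = 40: s = 50, a = 0.5, rise = 32 × 0.352/0.691 = 16.3 mmHg.
- μ = 200, σb = 30, σw = 20: rise = 0.1 mmHg.

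Net of this, worst of six minus last runs from about −49 mmHg (σw = 40, correlation 0, μ = 200) to about −6 mmHg (σw = 40, correlation 0.9, μ = 275: −22.2 + 16.3).

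**Dependence on time since dosing.** If correlation 0.9 carries across the first dose, then on day 1 in that last scenario the entry effect is about +5 rather than +16 mmHg, and the net is about −17 rather than −6 mmHg. The direction is unchanged but the size is not.

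**Route 2: representative readings.** No minimum is being taken, so the Route 1 bias does not arise. The possible bias comes from who chooses the readings and how, and the documents give nothing from which to size it.

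**Same rule at both ends.** With no true change and no entry selection, median of six against median of six, or worst against worst with equal counts, has expectation 0. With entry selection, median against median leaves 0 to +13 mmHg.

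**Precision.** SD of change in within-day SD units, for a median-of-six post-dose value:

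| Setting | Six-reading baseline | Single-reading baseline |
|---|---|---|
| Independent readings | 0.66 | 1.10 |
| Correlation 0.9, days independent | 1.30 | 1.36 |
| Correlation 0.9 carried across first dose, day 1 | 0.78 | 0.67 |

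The gain is not guaranteed, and on day 1 it can reverse.

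**The case against.** The strongest reply is that the choice of daily value is expressly assigned to a cohort 2 SAP, to be final before database lock. That stands: the missing summary rule is detail that the absent document may supply. A reader might infer that the choice will be made after the data are seen, but the documents show only that it must precede lock.

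A reader might also infer that the plan compares worst with last. It does not say so. Section 10.6.2 introduces the extra readings because P/F is the primary endpoint, so they may well be intended for it. Route 1 is therefore conditional.

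Nor do the documents show that suitable readings could never be recovered: "Respiratory status of patients is monitored hourly", and medical notes are source data (9.2), so a SAP could prompt further extraction. Four-hourly pre-dose readings are also taken where available; one is only the floor.

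A 24 h pre-dose window may be incomplete, because patients can enter after little more than 6 h in hospital or intubated. Extra extraction also cuts against cohort 2's aim of fewer timepoints (4.1). Both are fair costs. Finally, cohort 2 is descriptive and mainly meant to add safety data, and minor improvement is not a numerical threshold.

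What remains is stated protocol text: discretionary choice of readings without fixed times, and no common rule for the two ends of the change.

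**Conclusion.** The point holds as a cheap improvement that should be made, not as a demonstrated bias in a fixed analysis. Whichever post-dose readings are used, the present wording leaves a weakness: a daily minimum against an unselected value, or readings picked by unblinded staff. For the first, the expected spurious fall is 0.55 to 1.27 within-day SDs for the worst of six, before regression to the mean in the other direction. The mmHg ranges are illustrative. They rest on assumed SDs, means and correlations, and the net figures also on the eligibility reading being the last pre-dose reading. Confidence is medium, because the cohort 2 SAP may already settle the daily summary.

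The faulty cross-reference is clerical. It might suggest that cohort 2 has no defined baseline, but 7.1.1, 10.6.1 and Appendix 1 footnote a supply one.

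**What to change.** 1. In 7.5.1, 10.6.2 and Appendix 1 footnote a, replace the optional representative readings with readings at fixed clock times where available, for example the four-hourly times already used in cohort 1.
2. In 10.6.1, 10.6.2 and the cohort 2 SAP, name one daily summary, for example the median. Derive baseline by the same rule from whatever pre-dose readings exist in the 24 h before first dose, accepting fewer for patients admitted or intubated more recently. If the cohort 2 SAP already fixes the summary, cite it in 10.6.2.
3. Report worst against worst only as a sensitivity analysis, with the number of readings on each side.
4. As an editorial correction, point the cohort 2 endpoint baseline to 7.1.1 and 10.6.1.

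The cost is wording plus slightly more extraction from monitoring that is already hourly. Some pre-dose windows will be incomplete, some regression to the mean will remain, and precision may not improve, particularly on day 1 if readings are highly correlated.

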### **10.6.3 Secondary outcome analysis**

All secondary outcomes measured overtime will be summarised at each post-baseline timepoint, for each group, and overall where appropriate:

- Clinical status as assessed by a 7-point ordinal scale and change in clinical status
- Changes in lung compliance (computed in the database using tidal volume / (peak inspiratory pressure – PEEP)) from baseline and absolute values at day 5 (96 hrs ± 2 hrs), day 7 (144 hrs ± 4hrs), end of treatment, 3 and 5 days post end of treatment.
- The Mean daily Sequential Organ Failure Assessment (SOFA) score and change from baseline

The following secondary outcomes will also be summarised for each group, and overall, where appropriate:

- The number of oxygenation free days in the first 28 days
- Number of ventilator-free days in the first 28 days
- The incidence and number of days of new oxygen use, non-invasive ventilation or high flow oxygen devices in the first 28 days.
- Incidence and number of days of new mechanical ventilation use during the trial
- Intensive care unit (ICU) free days in the first 28 days
- In hospital mortality
- Length of ICU stay post treatment
- Length of ventilation
- Use of vasopressors

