Primary endpoints	
Efficacy
 
 
1. Change in <math>\text{PaO}_2/\text{FiO}_2</math> ratio from baseline(as defined in sections 7.1.2 and 7.1.3, daily during treatment, end of treatment and 3 and 5 days post treatment in the groups receiving rtPA)
 
 
Safety
 
 
1. Incidence and severity of major bleeding events directly attributable to the study drug
 
2. Decrease in fibrinogen levels to < 1.0 gm/L during treatment period and 48 hrs after the last dose of treatment
 
3. Number and nature of serious adverse events causally related to the treatment
 

Secondary objectives	
 
1. Investigate the impact on patient's clinical status over time using the WHO ordinal scale of clinical improvement.
 
2. Investigate the effect of nebulised rtPA on other respiratory markers (such as lung compliance) and organ dysfunction
 
3. Investigate the impact on in hospital mortality and resource utilisation
 
4.
 

Secondary endpoints	
 
1. Changes in lung compliance (defined as tidal volume / (peak inspiratory pressure – PEEP) ) from baseline (as defined in sections 7.1.2 and 7.1.3) and absolute values at day 5, day 7, end of treatment, 3 days post end of treatment and 5 days post end of treatment
 
2. Clinical status as assessed by a 7-point WHO ordinal scale at baseline (as defined in sections 7.1.2 and 7.1.3), daily up to 5 days post end of treatment and at day 28, discharge or death (whichever comes first)
 
3. Mean daily Sequential Organ Failure Assessment (SOFA) score at baseline (as defined in sections 7.1.2 and 7.1.3) and daily up to 5 days post end of treatment.
 
4. In follow up period, number of oxygenation free days, ventilator free days, intensive care stay, up to 28 days or death or discharge, whichever occurs first.
 
5. Incidence and number of days of new oxygen use, non-invasive ventilation or high flow oxygen devices in the first 28 days.
 
6. Incidence and number of days of new mechanical ventilation use during in the first 28 days
 
7. In hospital mortality
 

Exploratory objectives	Changes to coagulation and inflammatory markers concerning intervention and response to treatment.

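### Cohort 2 data extraction does not guarantee a lung-compliance reading inside the endpoint's own 96 h and 144 h windows

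*Protocol*

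**What the plan says.** **The endpoint.** Compliance is tidal volume divided by (peak inspiratory pressure minus PEEP). Protocol 10.2 and 10.6.3 both attach hour windows to two of its timepoints. The wording in 10.6.3 is "from baseline and absolute values at day 5 (96 hrs ± 2 hrs), day 7 (144 hrs ± 4hrs), end of treatment", followed by 3 and 5 days after treatment. Neither section restricts the windows to one cohort. The Summary (section 1) gives the same timepoints without hours: "absolute values at day 5, day 7, end of treatment, 3 days post end of treatment and 5 days post end of treatment".

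**Cohort 1 extraction (7.5.1).** "data points will be extracted for every four hours where available until 5 days after the last dose for cohort 1", with a floor of one point a day.

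**Cohort 2 extraction (7.5.1, repeated in 10.6.2 and Appendix 1 footnote a).** "For cohort 2 data will be extracted once a day coinciding with the worst PF ratio". The next sentence opens "As PF ratio is the primary endpoint" and provides for further points: "in addition to the worst PF ratio over the preceding 24 hrs up to a maximum of 6 data points spread across 24 hrs".

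**Variables.** The list after these rules marks sedation, paralysis, position and NEWS 2 as not collected in cohort 2. Tidal volume, peak inspiratory pressure and PEEP carry no such mark, and the purpose of the pressures is stated: "Peak inspiratory pressure (collected for computing compliance"). Compliance is therefore meant to be derived in cohort 2.

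**Source records.** "Respiratory status of patients is monitored hourly".

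**Baseline.** Protocol 10.6.1 uses the last available value before the first dose.

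**Analysis plan.** Protocol 10.6 promises a separate SAP for cohort 2. The SAP supplied follows protocol 7.0, which predates that cohort.

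**The concern.** The windows are clock times counted from the first dose. The one firm cohort 2 reading is timed by gas exchange, so nothing ties it to 96 h or 144 h. The extra points could close the gap, but a site that takes none of them still complies.

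Two things are at stake.

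- **Completeness.** Compliance is the first-listed secondary endpoint and the only one that measures lung mechanics directly. Cohort 2 is to supply at least 10 IMV patients, against 6 in cohort 1. If in-window readings are not extracted, the day 5 and day 7 summaries will rest on few patients or on readings outside the stated windows.
- **Comparability.** At the minimum, each on-treatment reading comes from the day's worst P/F hour, while baseline is simply the last value before dosing. If compliance tends to be lower when oxygenation is worst, change from baseline is pushed toward apparent worsening. This reaches all five post-baseline timepoints, including the three without an hour window.

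**Working it through.** The documents give no coverage figure for this endpoint, so there is none to reproduce. The question is how likely it is that at least one extracted reading falls in each window.

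**Inputs**
- Window widths (Protocol 10.2, 10.6.3): 96 ± 2 h is w = 4 h; 144 ± 4 h is w = 8 h.
- Required cohort 2 readings per day (7.5.1): 1, at the worst P/F.
- Extra readings per 24 h (7.5.1): m from 0 to 6.
- Cohort 2 IMV patients (4.1): at least 10. With 30 in total and at least 10 on non-invasive support, at most 20.
- Assumptions, not in the documents: the worst-P/F hour is uniform over 24 h; extra points are evenly spaced with a random starting phase; extra points carry the ventilator variables.

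**Step 1: required minimum (m = 0).** Probability = w/24.
- 96 h: 4/24 = 16.7%.
- 144 h: 8/24 = 33.3%.

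If extraction days are counted from the first dose, each window straddles two study days and the formula becomes 1 − (1 − (w/2)/24)². That gives 1 − (22/24)² = 16.0% and 1 − (20/24)² = 30.6%, so the result barely changes.

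**Step 2: expected counts at the minimum**, among IMV patients still ventilated at those times.
- n = 10: 10 × 0.167 = 1.7 at 96 h; 10 × 0.333 = 3.3 at 144 h.
- n = 20: 3.3 and 6.7.

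**Step 3: both windows covered, at the minimum.** This depends on how the worst hour behaves from day to day.
- Independent days: 0.167 × 0.333 = 5.6%, about 6%.
- Same worst hour every day: 96 h and 144 h are both whole days after the first dose, so the windows share a centre on the 24 h clock and the 4 h window lies inside the 8 h one. The joint probability is then 4/24 = 17%.

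**Step 4: adding m evenly spaced points.** Coverage = 1 − (1 − w/24) × (1 − min(1, m·w/24)).

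| m | 96 ± 2 h | 144 ± 4 h |
|---|---|---|
| 0 | 16.7% | 33.3% |
| 1 | 1 − (5/6)(5/6) = 30.6% | 1 − (2/3)(2/3) = 55.6% |
| 2 | 1 − (5/6)(4/6) = 44.4% | 1 − (2/3)(1/3) = 77.8% |
| 3 | 1 − (5/6)(3/6) = 58.3% | 100% |
| 4 | 1 − (5/6)(2/6) = 72.2% | 100% |
| 5 | 1 − (5/6)(1/6) = 86.1% | 100% |
| 6 | 100% | 100% |

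A simulation with 200,000 draws agrees: at m = 1 it gives 30.4% and 55.5%, and at m = 3 it gives 58.5% and 100%.

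**Step 5: uneven extra points.** If all seven readings (the worst plus 6) fall at independent random times, coverage is 1 − (20/24)⁷ = 72% and 1 − (16/24)⁷ = 94%. The maximum number of points therefore secures both windows only if they are evenly spread.

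**Step 6: using the hourly record.** The charted hour nearest a target time is at most 0.5 h away, well inside ± 2 h and ± 4 h. Coverage is then complete wherever the three variables were charted.

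**The case against.** A reader might infer that most cohort 2 compliance values will fall outside the windows, or that the endpoint cannot be derived in that cohort. The documents do not support either reading.

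- **The extra points count.** The protocol says further points will be extracted. One evenly spread extra point already gives a majority of patients a reading in the 144 h window, and three do so for the 96 h window.
- **They probably carry ventilator data.** The rationale given for them is the P/F ratio, but they sit under the same respiratory-status item as the variable list. That list flags what cohort 2 omits and does not flag tidal volume or the pressures. The natural reading is that the list covers every extracted point.
- **The source data should exist.** With hourly monitoring, in-window readings should be in the chart, and 10.2 and 10.6.3 tell staff which hours matter.
- **Reach is limited.** Only IMV patients are affected, and only two of five post-baseline timepoints have hour windows. Cohort 1's four-hourly extraction applies only where data are available and has the same one-a-day floor.
- **A cohort 2 SAP is promised.** It may set windows and rules for selecting readings.

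All of this stands, and it limits the point to a lack of assurance. It does not remove it. The extra points have a ceiling but no floor and no times, so in-window coverage is left to site practice. A SAP can widen a window or choose among readings, but an analysis rule cannot use readings that were never extracted.

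The selection effect is also fairly challenged: no passage links compliance to the hour of the worst P/F. It remains a plausible direction of bias without a size.

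**Conclusion.** The point holds as a mismatch between the endpoint definition and the cohort 2 extraction rule: a compliant site may or may not hold an in-window reading. If the worst-P/F hour is uniform, coverage runs from 17% to 100% at 96 h and from 33% to 100% at 144 h. The upper ends require evenly spread extra points that carry ventilator data. At the required minimum, between about 6% (independent days) and 17% (same worst hour daily) of patients would have both windows covered.

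The possible bias in change from baseline applies at that minimum, rests on compliance tracking oxygenation, and is not quantified.

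The consequence is modest. This is one secondary endpoint in the IMV patients of a cohort analysed separately and descriptively, as hypothesis-generating. Completeness and interpretability are affected; no power, error rate or decision rule is. The change is worth making because it is cheap.

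**What to change.** In Protocol 7.5.1 and Appendix 1 footnote a, add for cohort 2 IMV patients:

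- Extract tidal volume, peak inspiratory pressure and PEEP from the hourly record nearest 96 h and nearest 144 h after the first dose.
- Extract the same three variables at a fixed time, chosen independently of the P/F ratio, for end of treatment and for 3 and 5 days after it.
- Leave the baseline rule in 10.6.1 as it is.

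The cohort 2 SAP should then state that these readings, not the worst-P/F ones, feed the compliance endpoint. It should also report how many ventilated patients have a value at each timepoint.

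The cost is up to five extra chart extractions per ventilated patient, a sentence of protocol text and matching CRF fields. No new bedside procedure is needed. The fix cannot supply values for patients no longer ventilated at a timepoint, or where the three variables were not charted.
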